## 8.5 EFFECTIVENESS ANALYSES

Effectiveness analyses will be based on the Effectiveness population described in Section 8.4.2.

### 8.5.1 PRIMARY ANALYSES FOR THE EFFECTIVENESS PARAMETERS

The mean and standard deviation of MRCYL at Postop Month 3 and the corresponding 95% confidence interval will be calculated for the LAL treatment group. The mean and standard deviation of MRCYL at the Postop Month 6 visit and the corresponding 95% confidence interval will be calculated separately for the LAL historical control group and the Monofocal IOL historical control group. The Postop Month 3 outcomes of the LAL treatment group will be numerically compared and clinically assessed to the Postop Month 6 visits of the LAL historical control group and the Monofocal IOL historical control group. No formal statistical comparison will be performed.

In addition, the mean and standard deviation of the change in MRCYL from baseline (Visit #1/Adjustment #1) to Postop Month 3 and the corresponding 95% confidence interval will be calculated for the LAL treatment group. The mean and standard deviation of the change in MRCYL from baseline (Adjustment #1 (LAL)/17-21 days postop (Control)) to Postop Month 6 and the 95% confidence interval will be calculated separately for the LAL historical control group and the Monofocal IOL historical control group.

Clinical studies have shown that after standard phacoemulsification and IOL implantation, refractive stability of the eye has been observed as early as 2 months postoperatively. Additionally, studies in which a suture was needed to close the incision after intracapsular cataract surgery, it has been noted that the refraction in these eyes had stabilized sufficiently enough to allow prescription of first glasses at a mean time of 10.2 weeks after surgery. These documented time points of refractive stability provide evidence that the refractive results of the LAL at Postop Month 3 are stable enough to compare against the historical control groups at Postop Month 6.

### 8.5.2 ADDITIONAL EFFECTIVENESS ANALYSES

The following effectiveness outcomes will be summarized descriptively based on the observed data of the Effectiveness population, separately for the LAL treatment group, the LAL historical control group, and the Monofocal IOL historical control group. No imputation for missing values will be performed. The 95% confidence interval of the mean, if required, will be calculated based on the t-distribution; the 95% confidence interval of the proportion, if required, will be derived by the binomial distribution. It should also be noted that, for the MRCYL data analyses, the absolute MRCYL value will be used to present the summaries for simplicity.

 Baranyovits P. Stabilisation of refraction following cataract surgery. British Journal of Ophthalmology, 1988, 72, 815-819.

### 8.5.2.1 Manifest Cylinder (MRCYL)

The MRCYL will be summarized beginning at Adjustment #1 using descriptive statistics for continuous outcomes stratified by the LAL treatment group, the LAL historical control group, and the Monofocal IOL historical control group. The number and percent of eyes with a MRCYL of  $\leq 0.25$  D, 0.50, 0.75 D, 1.0 D, and  $> 1.0$  D at each visit observed by either the LAL treatment group, the LAL historical control group, or the Monofocal IOL historical control group will be reported.

### 8.5.2.2 Vector Difference

Error vector (EV) for the LAL treatment group will be presented as the vector difference between intended refractive correction (IRC) vector at Adjustment #1 and surgically induced refractive correction (SIRC) vector at Postop Month 3.

Error vector (EV) for the LAL historical control group will be presented as the vector difference between intended refractive correction (IRC) vector at Adjustment #1 and surgically induced refractive correction (SIRC) vector at Postop Month 6. For eyes in the LAL historical control group, the IRC will be the manifest refractive cylinder (0.5 D and MRaxis).

Error vector (EV) for the Monofocal IOL historical control group will be presented as the vector difference between intended refractive correction (IRC) vector at 17-21 days postop and surgically induced refractive correction (SIRC) vector at Postop Month 6. For eyes in the Monofocal IOL historical control group, the IRC will be the manifest refractive cylinder (0.5 D and MRaxis).

The mean magnitude of EV will be compared between the LAL treatment group, the LAL historical control group, and the Monofocal IOL historical control group.

The EV will be calculated for each eye based on Eydelman as follows:

IRC = For all subjects, the magnitude of the IRC is 0.5 D. The IRC axis is the manifest refractive cylinder axis as measured at the Adjustment #1/17-21 day visit.

SIRC = the vector difference between astigmatic correction vector at Adjustment #1 and 3 Months (LAL treatment group) or 17-21 day/Adjustment #1 visit and Postop Month 6 (LAL historical control group and Monofocal IOL historical control group)

EV = the vector difference between IRC at Adjustment #1 and SIRC at 3 Months (LAL treatment group) or 17-21 day/Adjustment #1 visit and Postop Month 6 (LAL historical control group and Monofocal IOL historical control group) (IRC – SIRC).

The mean and standard deviation of the magnitude of EV will be calculated along with the 95% confidence interval of the mean for the LAL treatment group at Postop Month 3 and for the LAL historical control group and Monofocal IOL historical control group at Postop

 Malvina B. Eydelman, et al. "Standardized Analyses of Correction of Astigmatism by Laser Systems That Reshape the Cornea", Journal of Refractive Surgery Volume 22 January/February 2006, pp 81-95

Month 6, separately. The outcomes will be numerically compared and clinically assessed. No formal statistical comparison will be performed.

#### **8.5.2.3 MRSE**

The measured MRSE, adjusted MRSE (to account for the measured distance of 4 meters) and change in MRSE from Adjustment #1 will be summarized by the descriptive statistics for continuous outcomes (such as mean and standard deviation) and the 95% confidence interval of the mean at each visit observed by subjects within the LAL treatment group, the LAL historical control group, and the Monofocal IOL historical control group respectively.

#### **8.5.2.4 Accuracy of MRSE**

The number and percent of eyes with a MRSE correction compared to the intended target within 0.25 D, 0.50 D, 0.75 D, 1.0 D, 1.25 D, 1.5 D, 1.75 D, and  $\geq 2.0$  D will be reported for the LAL treatment group at Postop Month 3 and for the LAL historical control group and Monofocal IOL historical control group at Postop Month 6. Additionally, the deviation of the achieved adjustment from the attempted adjustment will be summarized by the descriptive statistics for continuous outcomes by LAL treatment group, LAL historical control group, and Monofocal IOL historical control group.

The 95% confidence interval of the mean deviation and the 95% confidence interval of the proportion of eyes within 0.50 D and 1.00 D will be provided.

#### **8.5.2.5 Absolute MRSE**

The analyses methods described for the MRSE will be used for analyzing the absolute MRSE.

#### **8.5.2.6 Defocus Equivalent (DEQ)**

The DEQ, as defined as the absolute value of the MRSE error to target plus half the absolute value of the MRCYL, will be summarized descriptively at the Adjustment #1 visit and Postop Month 3 for the LAL treatment group and at the Adjustment #1/17-21 day visit and Postop Month 6 visit for the LAL historical control group and Monofocal IOL historical control group. The number and percent of eyes with DEQ  $\leq 0.5$  D and 1.0 D will also be summarized at the corresponding visit.

#### **8.5.2.7 Autorefraction**

Autorefraction sphere, cylinder, and spherical equivalent will be summarized descriptively at each visit observed by subjects within the LAL treatment group, the LAL historical control group, and the Monofocal IOL historical control groups respectively.

#### **8.5.2.8 Monocular Uncorrected Visual Acuity**

Monocular UCDVA will be presented with the number and percent of eyes that fall into each category of UCDVA at each visit observed by subjects within the LAL treatment group, the LAL historical control group, and the Monofocal IOL historical control groups respectively

(e.g. 20/20 or better, 20/25 or better, 20/32 or better, etc.). The logMAR UCDVA will be summarized by descriptive statistics for continuous outcomes for each visit. Change in UCDVA from the 17-21 day/Adjustment #1 visit will be presented at each visit as categorical outcomes of “increase of 15 letters or more”, “Increase of 10-14 letters”, “Increase of 5-9 letters”, “No change”, “Decrease of 5-9 letters”, “Decrease of 10-14 letters”, and “Decrease of 15 letters or more”. The change in logMAR UCDVA from the 17-21 day/Adjustment #1 visit will also be presented.

## **8.6 SAFETY PARAMETERS**

The following safety outcomes will be summarized descriptively based on the observed data of the Safety population. The 95% confidence intervals for means or percentage may be presented, as appropriate.

### **8.6.1 ADVERSE EVENTS (AE)**

For each adverse event, the number of reports, number and percent of subjects with the AE, and number and percent of eyes with the AE will be summarized at each postoperative visit. Serious ocular AEs and the non-ocular serious will be summarized in the same manner. Additionally, for each device-related AE reported during the study will be presented in the same manner.

### **8.6.2 MANIFEST CYLINDER (MRCYL)**

For all eyes in the Safety population, MRCYL will be summarized at the final scheduled visit using descriptive statistics for continuous outcomes stratified by the LAL treatment group, the LAL historical control group, and the Monofocal IOL historical control group. The number and percent of eyes with a MRCYL of  $\geq 1.00$  D and  $\geq 2.00$  D observed by either the LAL treatment group, the LAL historical control group, or the Monofocal IOL historical control group will be reported.

### **8.6.3 BCDVA**

For all eyes in the Safety population, the percentage of eyes that fall into each category of BCDVA at each visit (e.g. 20/20 or better, 20/25 or better, 20/32 or better, etc.) will be presented. In addition, the change in monocular BCDVA from the Adjustment #1 visit will be presented at each visit as categorical outcomes of “Increase of 15 letters or more”, “Increase of 10-14 letters”, “Increase of 5-9 letters”, “No change”, “Decrease of 5-9 letters”, “Decrease of 10-14 letters”, and “Decrease of 15 letters or more” for all eyes in the Safety Population. The mean change from the prior visit to the next visit will also be summarized in the same manner.

The listing of BCDVA and the possible reason for BCDVA loss of 10 letters or more will be provided for the eyes reported with a 10-letter or more loss in BCDVA from (1) pre-light treatment visit (Study Visit #1/Adjustment #1) to the final study visit (Postop Month 3) and (2) pre-light treatment visit (Study Visit #1/Adjustment #1) to any subsequent visit.

[REDACTED]

[REDACTED]

[REDACTED]

[REDACTED]

[REDACTED]

#### **8.6.6 UV PROTECTIVE EYEWEAR COMPLIANCE**

Periods of non-compliance with UV protective eyewear will be reported based on the number of periods and time of non-compliance.

#### **8.6.7 SUBJECTIVE SYMPTOMS AND COMPLAINTS**

Number and percent of subjects will be summarized at each reported subjective symptom for the Safety population.

#### **8.6.8 OTHER OCULAR EXAMINATIONS**

Slit lamp findings, fundus exam findings, and IOP including changes will be summarized descriptively for all eyes in the Safety population.

## 9 ADVERSE EVENTS

If an adverse event (AE) occurs, the first concern will be the safety and welfare of the subject; treatment should be provided as appropriate for the event. During the study, the Investigator should appropriately treat and follow each AE until it resolves, stabilizes, or it is determined that further improvement is not expected.

### 9.1 ADVERSE EVENT DEFINITIONS

An adverse event (AE) is any untoward medical occurrence, unintended disease or injury, or untoward clinical signs (including abnormal laboratory findings) in subjects, users, or other persons, whether or not related to the investigational medical device.

Note 1 to entry: This definition includes events related to the investigational medical device or the comparator.

Note 2 to entry: This definition includes events related to the procedures involved.

Note 3 to entry: For users or other persons, this definition is restricted to events related to investigational medical devices.

Unanticipated Adverse Device Effects (UADE) are any serious adverse effect on health or safety or any life-threatening problem or death caused by, or associated with a device, if that effect, problem, or death was not previously identified in nature, severity or degree of incidence in the investigational plan or application (including a supplementary plan or application), or any other unanticipated serious problem associated with a device that relates to the rights, safety, or welfare of subjects.

An investigator will submit to the Sponsor and to the reviewing IRB a report of any UADE occurring during an investigation as soon as possible, but in no event later than 10 working days after the investigator first learns of the effect. The Sponsor will immediately conduct an evaluation of any unanticipated adverse device effect. The results of the evaluation will be reported to FDA and to all reviewing IRB's and participating investigators within 10 working days of the Sponsor becoming aware of the event. Thereafter the Sponsor shall submit additional reports concerning the effect as FDA requests. If a UADE is determined by the Sponsor to present an unreasonable risk to study subjects, all investigations or parts of the investigation presenting that risk will be terminated as soon as possible. Termination will occur not later than 5 working days after this determination is made, and not later than 15 working days after first receiving notice of the event. The investigation will not be resumed without IRB and FDA approval.

All events that the investigator regards as clinically significant should be reported to ensure full reporting of all significant adverse events. The list below provides additional guidance on specific events that will need to be reported as AEs as specified.

1. Anterior Chamber Inflammation

- Iritis/cells/flare (if present after the Screening/Adjustment #1 visit and greater than grade 1 (trace)) or (any iritis/cells/flare present at Postop Month 3 of any grade) OR
- Chronic anterior uveitis (Persistent anterior segment inflammation characterized by grade 1+ cell or greater using Standardization of Uveitis Nomenclature criteria; present at the Postop Month 3 visit, or relapses in less than 3 months after discontinuation of therapy, or the subject is maintained on therapy for more than 3 months to control inflammation).

2. Corneal edema:

- If present after the Screening/Adjustment #1 visit and greater than grade 1 (trace)) or (if present at Postop Month 3 of any grade) OR
- Corneal swelling (stromal or epithelial) resulting in BCDVA  $\leq 20/40$  after Screening/Adjustment #1 visit)

3. Conjunctival hyperemia and/or edema:

- If present after Screening/Adjustment #1 visit and greater than grade 2 (mild)

4. Posterior capsular opacity (PCO) that requires YAG Capsulotomy treatment

5. Raised intraocular pressure (IOP)  $\geq 10$  mmHg above preoperative and greater than 25 mmHg (if present after Screening/Adjustment #1 visit) AND unrelated to mechanical pupillary block

6. Loss of BCDVA of  $\geq 10$  letters (when compared to Adjustment #1 BCDVA).

Per the Special Report: The American Academy of Ophthalmology Task Force Consensus Statement on Adverse Events with Intraocular Lenses, the following types of adverse events will be reviewed by the Sponsor to determine if they meet the following definitions for reporting purposes:

Adverse Event	Definition
Clinically significant cystoid macular edema	Macular edema diagnosed by clinical examination and adjunct testing (e.g., OCT, FA, or other method) resulting in reduced BCDVA to 20/40 or worse
Endophthalmitis	after Adjustment #1 Postoperative intraocular inflammation requiring vitreous tap and use of intraocular antibiotics
Mechanical pupillary block	A shallowing of the peripheral and/or central anterior chamber with or without elevation of IOP by obstruction of the flow of aqueous humor from the posterior chamber through the pupil to the anterior chamber. This may be induced by the crystalline lens, vitreous face, or implanted devices
Rhegmatogenous Retinal Detachment	Partial or complete retinal detachment associated with retinal tear
Toxic anterior segment syndrome	An acute, noninfectious inflammation of the anterior segment of the eye that develops within 24 to 48 hours after surgery and is characterized by corneal edema and accumulation of white cells in the anterior chamber of the eye
Secondary IOL intervention	Exchange: The investigational device is replaced with the same lens model. Removal: The investigational device is removed and replaced with a noninvestigational lens or no lens is implanted.
	Reposition: The existing IOL is surgically moved to another location or rotated.

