- A study eye at time of screening noted with an ocular adverse event that could be negatively impacted by light treatment or negatively impact the effectiveness or safety of a light treatment. This includes corneal edema and superficial punctate keratitis (SPK) (Grade 3 (moderate) or more severe)), retinal conditions including diabetic retinopathy and cystoid macular edema, epithelial defect, and endophthalmitis.
- A study eye with any ongoing adverse event.
- A study eye at time of screening noted with evidence of premature photopolymerization as evidenced as a zone on the lens surface.
- A study eye at time of screening noted with any evidence of posterior capsular opacity (PCO).

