## 9.6 IDENTIFICATION AND COLLECTION

Identification and collection of an AE begins after informed consent has been obtained and documented. Standard sources of identifying AEs include:

- direct observation by the Investigator or study team member
- asking the study participant a specific question (e.g., “Since your last visit, have you experienced any problems with your eyes or vision?”)
- unsolicited volunteering of information by the study participant (e.g., “Doctor, I have had numerous headaches since I started using this lens.”)

Ocular AEs, ocular SAEs, and systemic SAEs observed or elicited by the Investigator, reported by the subject, or resulting from a test result, etc., occurring during the clinical investigation must be documented. During the study, the Investigator should treat the study subject as appropriate to ensure his/her safety and welfare. Refer to Section 7.12.1 for additional information pertaining to ongoing AEs at subject exit.

Pre-existing conditions will not be considered AE/SAEs but will be collected at the Screening/Adjustment #1 Visit as medical history. A worsening of a pre-existing condition during the study should be documented as an AE and evaluated accordingly.

Hospitalization is a criterion for assessment of seriousness. Hospitalization in the absence of a medical AE is not in itself an AE. For example, the following reports of hospitalization without a medical AE should not be considered either an SAE or an AE:

- Planned hospitalization for a pre-existing condition without serious deterioration in health (e.g., planned knee replacement surgery)
- Social admission (e.g., subject has no place to sleep)
- Administrative admission (e.g., for yearly physical exam or elective procedures not related to the study)
- Optional admission not associated with a precipitation medical AE (e.g., for elective cosmetic surgery)

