In order to perform the lens adjustment or the lens lock-in procedures, the subject's pupil needs to be adequately dilated. If this cannot be accomplished for any reason, additional eye drops, injections into the eye, or surgery may need to be utilized to adequately dilate the pupil. If the pupil cannot be adequately dilated after these types of treatments, the LAL may need to be explanted. An unpredicted change in vision can occur resulting from ocular exposure to daylight or any other UV source before the LAL is locked-in. The light treatments may not improve vision and/or manifest refraction, and the adjustment/lock-in procedure may make vision worse, such that it may be necessary to remove and replace the LAL. Vision loss may be permanent and may not be improved by replacing the LAL. There is a potential risk for UV-induced damage to the eye, including the cornea and retina, which may be permanent. UV light can sometimes cause a reactivation of previous herpes virus infection in the eye. A reactivation of herpes virus can cause scarring of the cornea, blurred vision, eye pain, extreme light sensitivity, permanent loss of vision, and possible need for corneal transplant. Temporary or persistent erythropsia and/or temporary or persistent color vision deficiency may occur. Corneal dryness and corneal abrasions from the lens used for adjustment and lock-in can occur. After the lens adjustment(s) or after the lens lock-in procedures, discomfort, itching and light sensitivity may occur. In cases where a spherocylinder adjustment is performed, it is possible that visual disturbances may occur if the IOL rotates or if the correction is not performed on the correct axis of astigmatism.

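### For corneal edema or iritis present at Visit #1 and not worsening, sections 9.1 and 9.6 give opposite AE answers; and the 8.6.7 symptom count has no split at Visit #1

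*Combined protocol and SAP*

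**What the plan says.** **Graded signs.** Section 9.1 lists events that must be reported as AEs. For corneal edema the trigger is "If present after the Screening/Adjustment #1 visit and greater than grade 1 (trace)) or (if present at Postop Month 3 of any grade"). For iritis/cells/flare the first trigger is "if present after the Screening/Adjustment #1 visit and greater than grade 1 (trace"), with a second trigger of "any iritis/cells/flare present at Postop Month 3 of any grade". For conjunctival hyperemia or edema it is "If present after Screening/Adjustment #1 visit and greater than grade 2 (mild"). None of these three refers to the grade the eye had at Visit #1. The BCDVA item in the same list does: loss is measured from Adjustment #1.

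**Pre-existing conditions.** Section 9.6 states: "Pre-existing conditions will not be considered AE/SAEs but will be collected at the Screening/Adjustment #1 Visit as medical history". The next sentence makes worsening of such a condition an AE.

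**Exclusions.** Sections 1.5 and 6.2 exclude eyes with an ocular AE at screening that could interact with light treatment: "This includes corneal edema and superficial punctate keratitis (SPK) (Grade 3 (moderate) or more severe"). A further bullet excludes eyes with an ongoing AE (the synopsis adds the word ocular).

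**Symptoms.** Table 1 (section 7.10) records subject-reported symptoms at Visit #1 and at every later visit. The whole of section 8.6.7 is: "Number and percent of subjects will be summarized at each reported subjective symptom for the Safety population".

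**The concern.** Visit #1 falls 17 to 24 days after cataract surgery, so mild residual inflammation or edema at that visit is plausible. If such a sign persists without worsening, an investigator who follows 9.1 reports an AE and one who follows 9.6 records history. Two sites could then give different counts for identical eyes, and with 25 treated subjects each eye carries visible weight.

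The symptom count raises a related question. Section 9.12 warns that after a spherocylinder adjustment "it is possible that visual disturbances may occur if the IOL rotates" or if the correction is placed on the wrong axis. Subject-reported symptoms are one place where such a complaint would appear. A count that does not separate complaints present before treatment from those arising after it does not show what followed the 0.50 D treatment.

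The points affected are the all-cause counts of the listed graded signs and the symptom counts.

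**Working it through.** The plan gives no figure on this point, so there is nothing to reproduce. The check applies both rules to every possible grade path.

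**Inputs.** Grades 1 (trace), 2 (mild) and 3 (moderate) come from sections 9.1 and 6.2. Grades 0 (none) and 4 (severe) are assumed. A path is a Visit #1 grade *b* of at least 1, a later grade *p* from 0 to 4, and a timing (before Month 3, or at Month 3).

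**Rules.**
- 9.1, iritis or edema: AE if *p* > 1, or if *p* ≥ 1 at Month 3.
- 9.1, hyperemia: AE if *p* > 2.
- 9.6: AE only if *p* > *b*.
- Conflict: 9.1 says AE and 9.6 says not.

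**No exclusion applied** (*b* = 1 to 4; 4 × 5 × 2 = 40 paths).
- Iritis or edema before Month 3 needs 2 ≤ *p* ≤ *b*: 0 + 1 + 2 + 3 = 6. At Month 3 it needs 1 ≤ *p* ≤ *b*: 1 + 2 + 3 + 4 = 10. Total 16.
- Hyperemia needs 3 ≤ *p* ≤ *b*: 1 + 2 = 3 at each timing, so 6.

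**With the exclusions.**

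| Reading | Iritis or edema: conflicts / paths | Hyperemia: conflicts / paths |
|---|---|---|
| None applied | 16 / 40 | 6 / 40 |
| Grade 3 or worse excluded | 4 / 20 | 0 / 20 |
| Eyes above the 9.1 threshold at Visit #1 excluded as ongoing AEs | 1 / 10 | 0 / 20 |

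The four conflicts in the second row are grade 1 to 1 at Month 3, 2 to 1 at Month 3, 2 to 2 before Month 3, and 2 to 2 at Month 3. The one conflict in the third row is trace to trace at Month 3.

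**Where the rules agree.** If iritis or edema worsens from *b* ≥ 1, then *p* ≥ 2, so both rules say AE. For hyperemia, grade 1 to 2 is a worsening under 9.6 but below the 9.1 trigger (2 paths). That is a gap in the list and not a contradiction, because 9.1 presents the list as additional guidance.

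These are counts of logically possible paths, not expected numbers of eyes. The documents give no frequency of residual signs at Visit #1.

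**Weight of one eye.** 1/25 = 4.0% (exact 95% CI 0.1% to 20.4%).

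**Symptoms, with assumed inputs.** Let *k* of 25 subjects have a symptom at Visit #1 and 2 others develop it later. If Visit #1 reports are pooled in, the count is (*k* + 2)/25. The new count is 2/25 = 8%.

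| Assumed *k* | Pooled | New |
|---|---|---|
| 0 | 2/25 = 8% | 8% |
| 5 | 7/25 = 28% | 8% |
| 10 | 12/25 = 48% | 8% |

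The gap is *k*/25, so it depends entirely on Visit #1 prevalence.

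**The case against.** **The exclusions may do most of the work.** A natural example is grade 2 edema at Visit #1, still grade 2 at Adjustment #2. A reader might treat this as the standard case. The documents do not support that firmly: such an eye may be excluded as having an ongoing AE, and eligibility also requires BCDVA of 20/20 or better and clear media. The Grade 3 qualifier may even attach only to SPK, which would exclude edema of any grade. This stands as a limit on the conflict, but it does not remove it. Iritis is not named in that bullet, and trace at Visit #1 is below the 9.1 trigger, so trace iritis persisting to Month 3 is still classified both ways. Whether a sign that 9.6 calls pre-existing can also be an ongoing AE is not settled anywhere.

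**Hyperemia.** A reader might extend the conflict to it. Persistent grade 2 is not an AE under either rule, and no conflict is left if Grade 3 or worse eyes are excluded. The named list does not mention hyperemia, so this rests on extending the cut-off or on the ongoing-AE bullet.

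**The specific list could prevail over the general rule.** That is a reasonable reading of 9.1, but neither section says so.

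**Other provisions already help.** BCDVA change is measured from Adjustment #1 (8.6.3), AEs are summarized by visit with device-related AEs shown separately (8.6.1), and 8.6.8 summarizes slit lamp findings (its reference to changes may cover only IOP). A reader might conclude that all the safety counts are mixed; they are not.

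**Symptoms.** A reader might infer that 8.6.7 requires pre-treatment complaints to be kept in the count, or that a new disturbance could not be detected. Section 8.6.7 is silent on both, and the visit-level data allow the separation. Parts of 8.6 and a row of Table 1 are redacted, so other records of visual disturbance may exist.

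**Ocular versus any.** Both ongoing-AE bullets concern the study eye, so the wording difference is minor.

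**Scale.** The study is descriptive, with at most two sites, and no decision threshold depends on a 4-point shift. That is fair, and it is why this is a clarification and not a threat to the study's conclusions.

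**Conclusion.** The concern holds in a limited form. For corneal edema and iritis/cells/flare present at Visit #1 and then unchanged or improving, 9.1 and 9.6 classify the same eye differently and nothing says which prevails. The extent is 16 of 40, 4 of 20 or 1 of 10 grade paths, according to how the exclusions are read. Trace persisting to Month 3 conflicts in all three (for edema, unless edema of any grade is excluded). This rests on the assumed end grades 0 and 4 and on taking pre-existing to mean present at Visit #1.

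Separately, the symptom count in 8.6.7 has no stated visit or baseline split, so the planned table does not show which complaints are new after treatment. The 28% against 8% contrast is an illustration on assumed inputs. It keeps the same 25 subjects as denominator; 2/20 = 10%, among those free of the symptom at Visit #1, is a different quantity and should not be set against 28%.

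**What to change.** 1. **Sections 9.1 and 9.6.** The sponsor should reconcile the two for signs persisting from Visit #1 and state which rule governs. Keep the existing grade thresholds and keep persistent signs in the AE tables. Split each count of the graded signs into new or worse than Visit #1 and persisting from Visit #1. Replacing the thresholds with a bare new-or-increased rule would not serve: it would bring in new trace signs before Month 3 and drop persistent Month 3 inflammation from the table, and delayed recovery after light treatment would appear as exactly that persistence.
2. **Sections 1.5 and 6.2.** Reconcile the ongoing-AE bullets with the Grade 3 wording, and say whether a pre-existing sign can be an ongoing AE and which signs the grade applies to.
3. **Section 8.6.7.** Tabulate symptoms by visit, show Visit #1 prevalence, and report the number and percent new or worse since Visit #1 among all treated subjects.

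**Cost.** Wording in these sections and one extra split in the AE and symptom tables. Visit #1 slit lamp findings and symptoms are already scheduled, so no new data are needed.
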